2.6.3 Handling of missing values not related to intercurrent events

Handling of intercurrent events associated with key secondary objectives are described in the [Section 1.2.2](#). The missing data not related to intercurrent events for key secondary will be imputed based on the missing at random (MAR) assumption. The details of the imputation method are mentioned in [Section 5.4.1](#).

2.6.4 Other secondary endpoint analyses

Secondary endpoints which are not part of the testing strategy include:

- Proportion of participants tolerating a single dose of ≥ 1000 mg (2044 mg cumulative tolerated dose) of peanut protein without dose-limiting symptoms during DBPCFC conducted at Week 52

Number and percentage of responders at Week 52 will be summarized by treatment group in overall population. Number and percentage of responders at Week 52 may also be summarized by treatment group in the subset of responders at Week 12. Missing data of DBPCFC at Week 52 will not be imputed. The summary statistics will be provided for observed data.

- Change in maximum tolerated dose (MTD) of peanut protein without dose-limiting symptoms during the DBPCFC at Week 52 compared to Week 12

MTD at Week 52 along with changes from baseline and changes from Week 12 will be summarized descriptively. Missing data will not be imputed. The summary statistics will be provided for observed data.

- Change from baseline in MTD of peanut protein without dose-limiting symptoms during the DBPCFC at Week 12

An analysis of covariance (ANCOVA) model of change from baseline in log transformed MTD at Week 12 DBPCFC will be fit with terms for treatment group, age subgroup (12-17 years, 18-55 years), log-transformed total IgE at Screening Visit 1, region, and log-transformed MTD at baseline. Missing MTD at Week 12 values due to intercurrent events will be imputed by screening MTD, and other missing data will be multiply imputed under MAR assumption. If model assumptions of homoscedasticity and normality are not met, then the Wilcoxon rank-sum test may be performed.

- Change from baseline in peanut-specific IgE and IgG4 at Week 12, Week 16 and Week 52

Summary statistics, including geometric means and standard deviations, will be presented for peanut-specific IgE and IgG4 along with changes from baseline by time point and treatment group. The summary statistics will be provided for observed data. Change from baseline in log-

transformed levels of peanut specific-IgE and peanut specific-IgG4 at Week 12 and Week 16 will be analyzed using an ANCOVA model with terms for treatment group, age group, region, log-transformed total IgE at Screening Visit 1, and log-transformed baseline peanut specific-IgE or peanut specific-IgG4. Values below the LLOQ or above the ULOQ will be imputed as half the LLOQ or as the ULOQ, respectively.

- Change from baseline (screening) in mean wheal diameters by SPT to peanut at Week 16, Week 56 and Week 68

The mean is the average of wheal orthogonal diameter and wheal longest diameter minus the average of the non-missing negative control diameters. In most instances, the negative control diameters are 0mm.

Summary statistics will be presented by treatment group at each visit for:

- Undiluted peanut SPT
- Change from baseline in undiluted peanut SPT (mm)
- Percent change from baseline in undiluted peanut SPT
- Average across all dilutions
- Change from baseline across average of all dilutions (mm)
- Percent change from baseline across average of all dilutions

The summary statistics will be provided for observed data. Change from baseline in SPT mean wheal diameter at Week 16 will be analyzed using an ANCOVA model with terms for treatment group, age subgroup, region, log-transformed total IgE at screening, and baseline mean wheal diameter. This analysis will be performed for undiluted peanut SPT and the average across all dilutions (i.e. 1/100000, 1/10000, 1/1000, 1/100, 1/10, and undiluted). Note that the undiluted values are included in the average across all dilutions.

The analyses of PRO endpoints are described in [Section 2.10](#).

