### 16.5.3 Starting the Skin Prick Test

- Location of SPT: The skin of the participant's back is the preferred site of testing, alternatively the forearm may be used. For consistency purposes it is important for individual participants to perform the SPT at the same site during the study.

*EXAMPLE:*

*TSPT: if the participant had a positive medical history of milk and egg in addition to peanut, total 10 pricks are needed; positive control, negative control, peanut (extract), peanut (1:10), peanut (1:100), peanut (1:1'000), peanut (1:10'000), peanut (1:100'000), milk, and egg*

- Test time: Skin reactions should be recorded after 15 minutes of dropping allergen to the pricked location.
- Positive/negative control: The SPT should be repeated if the valid positive ( $\geq 3$  mm wheal) and negative (no response) control results were not obtained.
- Prohibited/washout medications prior to SPT

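### The skin prick wheal subtracts the negative control with no floor at zero, and the SAP does not say that a repeat test replaces one with failed controls

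*SAP*

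**What the plan says.** SAP 2.6.4 defines the analysed wheal as the average of the longest and orthogonal diameters "minus the average of the non-missing negative control diameters. In most instances, the negative control diameters are 0mm". The document history shows that the negative-control calculation was specified in the September 2023 update, before database lock.

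Two measures are built from this definition: undiluted peanut, and the average over six concentrations (undiluted and five ten-fold dilutions). On the second, the SAP says "Note that the undiluted values are included in the average across all dilutions". Both are summarised as values, mm change and percent change; one listed item is "Percent change from baseline in undiluted peanut SPT". For the summaries, "The summary statistics will be provided for observed data". A Week 16 ANCOVA is fitted to the change in mean wheal diameter for both measures, with the baseline wheal as a covariate.

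Protocol 16.5.3 gives sites a control rule. It opens "The SPT should be repeated if the valid positive", sets the positive-control wheal at 3 mm or more, and closes "negative (no response) control results were not obtained".

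SAP 2.6.4 does not mention a lower limit for the corrected diameter, the positive control, or which test is used when an SPT was repeated.

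**The concern.** Under Protocol 16.5.3 a valid negative control shows no response. On such a test the SAP's subtraction removes 0 mm. The subtraction changes a result only when the control did respond, which is when the protocol asks for a repeat. By saying that controls are 0 mm in most instances, the SAP allows for some non-zero controls in the analysed data, and it gives no rule that puts the repeat in their place.

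A wheal cannot be smaller than 0 mm. Followed literally, the derivation gives a negative diameter at every concentration whose wheal is below the control. These values enter the six-concentration average, its mm change in the Week 16 ANCOVA and, when the control response is at screening, the baseline covariate. The percent-change summary can pass -100%, be undefined, or have the wrong sign.

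**Working it through.** **Inputs**
- Wheal at one concentration: w = (longest + orthogonal)/2 (SAP 2.6.4; Protocol 16.5.3.1).
- Corrected diameter: d = w - c, where c is the mean negative-control diameter (SAP 2.6.4).
- Six concentrations per average (SAP 2.6.4).
- Percent change = 100 x (post - baseline)/baseline. This is the usual formula; the SAP does not write it out.
- Neither document gives wheal or control data, so all wheals and values of c below are assumptions. The SAP definition is read as applying to each concentration.

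**1. The documents' own figure.** The example in Protocol 16.5.3.1 is (15 + 8)/2 = 11.5 mm, which reproduces. It shows no control subtraction.

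**2. Algebra.** The mean of (w - c) over six concentrations is mean(w) - c. Without a floor the average falls by the full c, whatever the peanut wheals are. Subtracting at each concentration or once from the average gives the same number.

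**3. Wheals unchanged between visits.** Wheals 8, 5, 2, 0, 0, 0 mm; baseline control 0 mm; baseline average 15/6 = 2.5 mm.

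| Week 16 control | SAP average | Change | Floored average | Change |
|---|---|---|---|---|
| 0 mm | 2.5 mm | 0% | 2.5 mm | 0% |
| 2 mm | (6+3+0-2-2-2)/6 = 0.5 mm | -80% | (6+3)/6 = 1.5 mm | -40% |
| 3 mm | (5+2-1-3-3-3)/6 = -0.5 mm | -120% | (5+2)/6 = 1.17 mm | -53% |

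The floor removes the impossible values and roughly halves the distortion. Only a test with a valid control removes it entirely.

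**4. Strong reduction at Week 16.** Baseline 10, 8, 6, 3, 0, 0 mm (average 27/6 = 4.5); Week 16 wheals 2, 0, 0, 0, 0, 0 mm.
- c = 0: average 2/6 = 0.33 mm, -92.6%.
- c = 1: average (2 - 6)/6 = -0.67 mm, -114.8%. Floored: 1/6 = 0.17 mm, -96.3%.
- c = 2: average (2 - 12)/6 = -1.67 mm, -137.0%. Floored: 0 mm, -100%.

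Here the average passes -100% with a 1 mm control. Undiluted peanut alone does so only once c exceeds its 2 mm wheal (c = 3: -1 mm, -110%).

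**5. Control response at screening.** Take a corrected undiluted wheal of 4 mm (the eligibility minimum in Protocol 5.1) and no wheal at the other five concentrations. The baseline average is (4 - 5c)/6.
- c = 0.8: the average is 0, so percent change is undefined.
- c = 2: the average is -1.0 mm. A later average of 0 mm is a rise of 1 mm but is reported as 100 x (0 + 1)/(-1) = -100%.
- Floored, the baseline average is 4/6 = 0.67 mm in both cases.

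**6. Effect on an arm mean.** By step 2, one affected test moves an arm's mean by c/n. With c = 2 mm and the roughly 23 placebo participants in SAP 3.1, that is 2/23 = 0.09 mm per test. The number with a Week 16 SPT is not given. Under the halt arrangements in SAP 1.1 it is likely to be below 23, which would make the shift per test larger.

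**The case against.** The strongest reply is that the subtraction is sensible and the illustrations are the unfavourable case. Protocol 5.1 itself judges the wheal against the negative control. Protocol 16.5.2 and 16.5.3.1 make the dilutions with saline and use saline as the negative control, so a non-specific response should also appear at the peanut sites. If it adds 2 mm at every site, wheals of 10, 7, 4, 2, 2, 2 mm less 2 mm average 2.5 mm and nothing is distorted. If each site shows the larger of the two responses, 8, 5, 2, 2, 2, 2 mm less 2 mm average 1.5 mm, which equals the floored result. This stands as a limit on how often negative diameters will arise. It does not argue against a floor, which changes nothing in either case.

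Further points stand in part:
- A reader might infer that percent change is tested. It is only summarised; the ANCOVA is on mm change, which does not need non-negative values. The mm change is still shifted by c.
- A reader might infer that the SAP analyses tests the protocol excludes. Protocol 16.5.3 tells sites to repeat; it sets no analysis exclusion. If repeats are always done and used, the problem disappears, but the SAP does not say so.
- A reader might infer that antihistamine-suppressed tests will be counted as treatment effect. Protocol Table 16-9 requires washout before the SPT, so the documents do not support expecting this.
- SAP 2.11 refers to a separate biomarker plan, not available here, which may hold such rules. The same section places the SPT analysis among the other secondary endpoints of this SAP.
- Flooring cuts off error on one side only. That is a fair cost, and a reason for the sensitivity analysis.

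**Conclusion.** The point holds as a defect in a stated derivation. With a non-zero control, the rule can give negative diameters, an average lowered by the full control value, and percent changes that exceed -100% or are undefined. This rests on reading the definition as applying to each concentration and on non-zero controls reaching the analysis.

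The size at group level cannot be computed, because neither document says how many controls are non-zero or how many concentrations show no wheal. Most controls are expected to be 0 mm and SAP 2.6.4 puts the endpoint outside the testing strategy, so the impact is probably small. No primary or key secondary conclusion depends on it.

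A reader might infer that the Week 16 SPT comparison is biased in favour of ligelizumab. The documents do not support that. Sites are blinded and the screening SPT precedes randomisation, so control responses should act mainly as noise across arms.

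**What to change.** Amend SAP 2.6.4 and apply the same rules at screening and at Weeks 16, 56 and 68:

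1. Where an SPT was repeated under Protocol 16.5.3, analyse the repeat with valid controls.
2. Set each control-corrected diameter to max(0, wheal - control) before averaging across concentrations. Tests with a control response and no valid repeat stay in the main analysis under this rule.
3. Add a sensitivity analysis limited to tests that meet both protocol criteria: positive control at least 3 mm, negative control with no response.

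The cost is a few lines of derivation and SAP text, and fewer participants in the sensitivity analysis. Reporting the number of tests with a non-zero negative control by arm and visit would show whether the issue mattered.

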2.7 Safety analyses

All safety endpoints (i.e. AEs, laboratory data, vital signs, and ECG) will be summarized by treatment for all participants on the safety set. In addition, subgroup analysis by age (12-17 years, 18-55 years) will be evaluated for most of the safety endpoints listed in this section. The safety analyses will be performed by the treatment groups for the three pooling periods as described in Section 2.1.1.1, unless otherwise specified.

2.7.1 Adverse events (AEs)

Unless otherwise specified, summaries will include treatment-emergent adverse events (TEAEs) only. Treatment emergent adverse events are defined as events started after the first dose of study treatment and within 16 weeks after the last study treatment, or events present prior to the first dose of study treatment but increased in severity based on preferred term within 16 weeks after the last study treatment. All events that the investigator classifies as reactions associated to the DBPCFC or SPT will not be included in reporting of treatment-emergent AEs and may be reported separately. The number and percentage (with exact binomial 95% CIs) of participants with TEAEs will be summarized in the following ways:

- by treatment, primary system organ class and preferred term.
- by treatment, primary system organ class, preferred term and maximum severity.
- by treatment, Standardized MedDRA Query (SMQ) and preferred term.

Separate summaries will be provided for study treatment-related adverse events, death, serious adverse events, other significant adverse events leading to discontinuation and TEAEs with potential cause of accidental exposure or ingestion. If a participant reported more than one AE with the same preferred term, the AE with the greatest severity will be presented. If a participant reported more than one AE within the same primary system organ class, the participant will be counted only once with the greatest severity at the system organ class level, where applicable.

For the legal requirements of ClinicalTrials.gov and EudraCT, two required tables on TEAEs which are not SAEs with an incidence greater than a certain threshold based on the final database and on TESAEs and SAEs suspected to be related to study treatment will be provided by system organ class and PT on the safety set population.

If for a same patient, several consecutive AEs (irrespective of study treatment causality, seriousness and severity) occurred with the same SOC and PT:

- a. a single occurrence will be counted if there is ≤ 1 day gap between the end date of the preceding AE and the start date of the consecutive AE
- b. more than one occurrence will be counted if there is > 1 day gap between the end date of the preceding AE and the start date of the consecutive AE

For occurrence, the presence of at least one SAE / SAE suspected to be related to study treatment / non-SAE has to be checked in a block e.g., among AE's in a ≤ 1 day gap block, if at least one SAE is occurring, then one occurrence is calculated for that SAE.

The number of deaths resulting from SAEs suspected to be related to study treatment and SAEs irrespective of study treatment relationship will be provided by SOC and PT.

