5. Action taken regarding with study treatment. All adverse events must be treated appropriately. Treatment may include one or more of the following:
  - Dose not changed,
  - Drug interrupted/permanently discontinued.

- Dose increases or reductions are not permitted.
6. Its outcome: not recovered/ not resolved; recovered/ resolved; recovering/ resolving; recovered/ resolved with sequelae; fatal or unknown

Conditions that were already present at the time of informed consent should be recorded in medical history of the participant.

Adverse events (including lab abnormalities that constitute AEs) should be described using a diagnosis whenever possible, rather than individual underlying signs and symptoms.

Adverse event monitoring should be continued until the end of study visit or for at least 30 days or 5 half-lives following the last dose of study treatment, whichever is longer.

Once an adverse event is detected, it must be followed until its resolution or until it is judged to be permanent (e.g. continuing at the end of the study), and assessment must be made at each visit (or more frequently, if necessary) of any changes in severity, the suspected relationship to the interventions required to treat it, and the outcome.

Information about adverse drug reactions for the investigational drug can be found in the Investigator's Brochure (IB).

Abnormal laboratory values or test results constitute adverse events only if they fulfill at least one of the following criteria:

- they induce clinical signs or symptoms
- they are considered clinically significant
- they require therapy

Clinically significant abnormal laboratory values or test results must be identified through a review of values outside of normal ranges/clinically notable ranges, significant changes from baseline or the previous visit, or values which are considered to be non-typical in participant with the underlying disease. Alert ranges for laboratory and other test abnormalities are included in [Section 16.1](#).

Please refer to [Section 16.4](#) for the assessment, reporting and management of hypersensitivity reactions observed during the DBPCFC and the post-DBPCFC observation period.

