Suspected Unexpected Serious Adverse Reactions (SUSARs) will be collected and reported to the competent authorities and relevant ethics committees in accordance with EU Guidance 2011/C 172/01 or as per national regulatory requirements in participating countries.

Screen Failures: SAEs occurring after the participant has signed the ICF until the time the participant is deemed a Screen Failure must be reported to Novartis.

Randomized or treated participants: SAEs occurring after the participant has signed the ICF until 120 days (5 half-lives of ligelizumab) after the participant has withdrawn consent or discontinued study must be reported to Novartis.

Please refer to [Section 16.4](#) for the assessment, reporting and management of serious hypersensitivity reactions observed during the DBPCFC and the post-DBPCFC observation period.

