### **Adverse events**

Treatment emergent adverse events are defined as events started after the first dose of study treatment or events present prior to the first dose of study treatment but increased in severity based on preferred term. All events that the investigator classifies as reactions associated to the DBPCFC or SPT will not be included in reporting of treatment-emergent AEs. The number (and percentage) of participants with treatment emergent adverse events will be summarized in the following ways:

- by treatment, primary system organ class and preferred term.
- by treatment, primary system organ class, preferred term and maximum severity.
- by treatment, Standardized MedDRA Query (SMQ) and preferred term.

Separate summaries will be provided for study treatment related adverse events, death, serious adverse events, other significant adverse events leading to discontinuation. If a participant reported more than one AE with the same preferred term, the AE with the greatest severity will be presented. If a participant reported more than one AE within the same primary system organ class, the participant will be counted only once with the greatest severity at the system organ class level, where applicable.

All AEs with onset in the follow-up period will also be considered as treatment emergent. Data from the placebo arm after switching to ligelizumab will be summarized separately. The number and percentage of participants with treatment emergent adverse events of special interest will be summarized by risk category, preferred term and treatment.

In addition, summaries will be provided by subgroups of age and allergy status (mono-sensitized and poly-sensitized).

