3. **Post-treatment follow-up period (Duration of 16 weeks):** There are 4 planned clinic visits (every 4 weeks). Study evaluations include safety, [REDACTED], post-treatment biomarkers. Study treatment is not given and there is no DBPCFC.

At the start of the study, recruitment was restricted to 12 - 55 year old participants. When approximately 60 adolescent participants (defined as 12 -17 years of age) would have completed all Week 12 assessments, an interim analysis [REDACTED] was to be performed for confirmation of the pediatric dose (safety will be reviewed by a Data Monitoring Committee - DMC). Independent sponsor members who are responsible for [REDACTED] Modeling & Simulation will be unblinded to the results of this interim analysis.

As Novartis decided to halt recruitment (Date of issuing halt notification: 05 Apr 2023) with the intention to terminate the study early, there will be no recruitment of children under age 12.

Patients who are already in the study (i.e., signed informed consent) at the time of the halt notification will be managed according to their individual progress within the study as described in the table below.

[figure not shown]
Group 1	Already completed Week 52 Visit assessments	Complete the 16-week safety follow up period as per protocol
Group 2	Already completed Week 12 Part 2 Visit	Attend the next scheduled visit (as per schedule of events), which will now correspond to the end of treatment visit (Week 52 Part 1). Patients will be informed at that visit that the treatment is stopped (no drug administration at that visit) and that they will enter the 16-week follow up period as per protocol. Notably, no oral food challenge will be done at this end of treatment visit
Group 3	Randomized but have not yet reached the Week 12 Part 2 Visit	At their next visit, investigators should inform the patient of the study status and provide them with the opportunity to continue and perform the assessments until week 12 Part 2. The week 12 Part 2 visit will now be considered end of treatment (Week 52 Part 2) so that afterwards patients will then enter the 16-week safety follow up period as per protocol. In this situation, there is no need to fill out the "Trial Feedback Questionnaire."
Group 4	Reached the Screening Visit 2 Part 1	Allowed to complete the Screening Visit 2 Part 2 (i.e., complete both parts of the baseline Oral Food Challenge) and, pending final eligibility, to be randomized and continue as patients in Group 3.

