2.4 Treatments (study treatment, rescue medication, concomitant therapies, compliance)

2.4.1 Study treatment / compliance

The duration of exposure in weeks to each treatment group will be summarized using descriptive statistics.

Duration of exposure to study treatment will be calculated as the number of weeks between the first dose date and the last dose date exposed to that treatment over the specified period (Duration of exposure = (date of last known study treatment – date of first known study treatment + 28)/7).

In addition, the number of doses, total cumulative dose and number of missed doses will be presented. Categorical data will be summarized as frequencies and percentages. For continuous data, mean, standard deviation, median, 25th and 75th percentiles, minimum and maximum will be presented.

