2.7.1.1 Exposure-Adjusted Incidence Rate

The crude incidence rate is defined as the percentage of participants with a specific adverse event divided by the total number of participants in each study group.

Due to expected differences in exposure and follow-up due to varied duration of study participation between participants, adverse event incidence rates will be provided as “exposure adjusted AE incidence rates” in addition to the crude incidence.

The EAIR is defined as the number of participants with a specific event divided by the total exposure-time among the participants in the study group. That is, the EAIR is calculated as:

$EAIR = n / \sum t_i$, where n is the number of participants having the i^{th} type event, and t_i is a participant's exposure time and defined as the shortest of the following:

1. time to the first episode of the i^{th} type event (if the event occurs),
2. time to the end of observation period, or
3. duration of study treatment plus the 16-week washout period (approximately corresponding to five half-lives) after last treatment dose

The total exposure time of all participants in a treatment group is $\sum t_i$. The EAIR is interpreted as the number of events occurring in a population per unit time. The exact Poisson 95% confidence interval for the EAIR will be provided as well, where an exact $100*(1-\alpha)\%$ confidence interval will be derived as follows (Garwood 1936, Sahai and Khurshid 1993):

- Lower confidence limit $L = \frac{0.5C_{\alpha/2,2n}}{\sum t_i}$ for $n>0$, 0 otherwise,
- Upper confidence limit $U = \frac{0.5C_{1-\alpha/2,2n+2}}{\sum t_i}$,

where $C_{\alpha,k}$ is the α th quantile of the Chi-square distribution with k degrees of freedom.

Whenever applicable, exposure adjusted incidence rates will be provided for the type as below:

1. TEAE: Primary SOC level, PT level

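### The SAP's 16-week cut-off for treatment-emergent AEs drops the last four weeks of follow-up for halt Group 2, contrary to the protocol and undeclared in SAP Section 4

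*SAP*

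**What the plan says.** SAP 2.7.1 defines treatment-emergent AEs as "events started after the first dose of study treatment and within 16 weeks after the last study treatment", plus events present before the first dose that worsen within the same limit. It adds: "Unless otherwise specified, summaries will include treatment-emergent adverse events (TEAEs) only". Protocol 12.5.2, under Adverse events, has no such limit: "All AEs with onset in the follow-up period will also be considered as treatment emergent".

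The halt table in SAP 1.1 sets the remaining schedule by group. For Group 2 (Week 12 Part 2 already completed), the next scheduled visit becomes the end-of-treatment visit: "Patients will be informed at that visit that the treatment is stopped (no drug administration at that visit"). The 16-week follow-up starts only after that visit.

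For the exposure-adjusted incidence rate (EAIR), SAP 2.7.1.1 takes the shortest of three times, one of which is "duration of study treatment plus the 16-week washout period (approximately corresponding to five half-lives) after last treatment dose". SAP 2.4.1 gives the only explicit duration formula: "Duration of exposure = (date of last known study treatment – date of first known study treatment + 28)/7".

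SAP Section 4, which lists departures from the protocol's analyses, does not mention the narrower AE window. The SAP document history for the 28 July 2023 revision records only that detail was added on treatment-emergent AEs. That revision also introduced the description of the halt.

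**The concern.** The cut-off and the halt schedule were revised together, but they do not fit each other. Protocol 10.1.1 requires AE monitoring "until the end of study visit or for at least 30 days or 5 half-lives following the last dose of study treatment, whichever is longer", so Group 2's AEs are collected through EOS. The analysis then discards the last part of what was collected.

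The lost interval contains the EOS visit. In Table 8-1, EOS is the only follow-up visit with haematology, chemistry, ECG, urinalysis and a stool sample. Stool results stay in the source documents, so a positive EOS stool test reaches the analysis database only as an AE. Helminthic infection is a named AE of special interest in SAP 2.7.1.2. Protocol 8.4.4 has the routine sample taken in the week before EOS, about days 133-140 after the last dose in Group 2. An infection dated to that sample would be missing from the treatment-emergent and special-interest tables. The registry table of non-serious AEs is also built on treatment-emergent events.

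**Working it through.** **Inputs**
- Cut-off: 16 weeks = 112 days after the last dose (SAP 2.7.1).
- Dosing interval: 4 weeks = 28 days (protocol Section 3).
- Follow-up visits: Days 393, 421, 449 and 477 (protocol Table 8-1).
- Dose given on Part 1 of Weeks 12 and 52, with Parts 1 and 2 about 1-7 days apart (protocol 16.4.2).
- Halt rules by group (SAP 1.1).

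**1. Reproduce the planned schedule.** Study day = 7 × week + 1. Week 56 gives 393 and Week 68 gives 477, as printed. Week 52 gives 365. EOS minus the Week 52 dose = 477 - 365 = 112 days. As planned, the cut-off and EOS fall on the same day and the two rules agree.

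**2. Apply the halt table.**

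| Group | Last dose to start of follow-up (days) | Last dose to EOS (days) | Beyond day 112 |
|---|---|---|---|
| 1 | 0 | 112 | 0 |
| 2 | 28 | 28 + 112 = 140 | 28 |
| 3 and 4, follow-up counted from Part 1 | 0 | 112 | 0 |
| 3 and 4, follow-up counted from Part 2 | 1-7 | 113-119 | 1-7 |

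Group 2's four follow-up visits fall 56, 84, 112 and 140 days after the last dose. The whole last interval, days 113-140, lies outside the window: 28/140 = 20% of the observation after the last dose. If the dose before the end-of-treatment visit was also missed, EOS is at 56 + 112 = 168 days and 56 days lie outside.

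**3. Which pool is affected.** Group 2's last dose is at Week 12 at the earliest, so the excluded days begin no earlier than Week 12 + 16 = Week 28. The Week 8 and Week 16 placebo-controlled pools in SAP 2.1.1.1 are untouched. Only the entire-study pool is affected.

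**4. EAIR denominator.** There are two readings of treatment duration:
- First dose to last dose: time at risk ends at last dose + 112 days and matches the numerator.
- The 2.4.1 formula with its extra 28 days: time at risk runs to 28 + 112 = 140 days after the last dose, but no event after day 112 can count. For an event-free Group 2 participant the surplus is 28/(84 + 28 + 112) = 28/224 = 12.5% of person-time if the last dose was at Week 12, and 28/(336 + 28 + 112) = 28/476 = 5.9% if it was at Week 48.

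SAP 2.7.1.1 does not say which reading applies.

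**The case against.** The strongest reply is that 16 weeks is a reasoned window with little practical effect. Protocol 4.1 itself equates 16 weeks of follow-up with five half-lives, and on the planned schedule the window lost nothing. The placebo-controlled pools cannot be affected, and the same window applies to both doses in the remaining pool. Restoring the protocol rule has a price: participants who stop treatment early are encouraged to attend all remaining visits, so events many months off drug could count as treatment-emergent. All of this stands. It limits the size of the point and argues for keeping the 16-week window as a second view. It does not explain why the SAP departs from the protocol without saying so.

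Four stronger readings are tempting, but the documents do not support them:

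- *Anything first found at EOS is lost.* The rule uses onset or worsening, not detection. An event that began by day 112 still counts.
- *These findings vanish from the safety reporting.* Laboratory summaries cover every visit, with maxima and minima from any post-baseline visit (SAP 2.7.3). ECG shift tables cover all post-baseline worsening (2.7.4.1). All deaths are listed (2.7.2), as are adjudicated events (2.7.1.2). Table 2-2 includes a deaths-and-SAEs output separate from the treatment-emergent SAE tables.
- *Groups 3 and 4 lose their EOS visit too.* The halt table maps Week 12 Part 2 to Week 52 Part 2 and then follows the protocol, where EOS is 112 days after the dose. An excess of 1-7 days arises only if follow-up is counted from Part 2.
- *The window is shorter than the protocol's five half-lives.* The 120-day figure in protocol 10.1.3 governs SAE reporting and runs "until 120 days (5 half-lives of ligelizumab) after the participant has withdrawn consent or discontinued study must be reported". It does not run from the last dose and does not define an analysis window.

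**Conclusion.** The point holds for Group 2. On nominal dates, AEs that start on days 113-140 after the last dose are treatment-emergent under the protocol, are collected, and are excluded from the treatment-emergent tables for the entire-study pool. The exclusion is 28 days per Group 2 participant who completes follow-up, and SAP Section 4 does not declare it.

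This rests on visits at their nominal days and no missed dose before the halt. Group 2's size is not given, so neither the number of events lost nor any shift in a rate can be computed. No bias between doses is shown. The EAIR mismatch is conditional on the 2.4.1 formula being used, and the natural reading of 2.7.1.1 avoids it. The point is a moderate one, worth correcting before database lock because it is cheap and concerns late safety events.

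**What to change.** - **SAP 2.7.1:** restore the protocol rule, so that AEs with onset or worsening after the first dose and through the end of the follow-up period (EOS visit) are treatment-emergent.
- **SAP 2.7.1.1:** end person-time at the same date and state that the extra 28 days in the 2.4.1 formula are not added, so that numerator and denominator share one window.
- **If the 16-week window is kept:** present it as a secondary table and list it in Section 4 with its reason.

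Moving the cut-off to last dose + 20 weeks would cover Group 2 only when no earlier dose was missed; the protocol rule covers both cases.

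The cost is SAP wording and one date derivation, with no new data collection. The downside is that some late off-drug events, mainly in participants who stopped treatment early, will count as treatment-emergent. The secondary 16-week table lets a reader see how much they matter.
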